STUDY PROTOCOL AND STATISTICAL ANALYSIS PLAN

Study title: A Randomized Controlled Trial to Investigate the Cognitive, Mood, Anti-inflammatory and Metabolic Effects of Chronic Oyster Mushroom Intervention in Older Adults.

Acronym: OYSCOG

Date: 01 October 2023

The Pleurotus oyster species is a common edible mushroom rich in ergothioneine, a bioactive compound with known neurocognitive benefits. The aim of the OYSCOG is to investigate the chronic effect (12-weeks) of the equivalent 1 portion of ergothioneine-rich Pleurotus oyster mushrooms (in dried powdered form) on cognition and mood, with examination of the potential inflammatory, metabolic, and neurological related mechanisms that may underlie these effects.

1. Sample Size Calculation

A power calculation based on similar research investigating the chronic benefits of other mushroom interventions on cognitive function suggests that 72 participants should give sufficient statistical power (with $\alpha=0.05$, $\beta=0.80$, Cohen's $d=0.60$). This calculation was based on the average Cohen's d value obtained from 7 RCTs examining the effect of Lion's Mane (Mori et al., 2009; Saitsu et al., 2019; Li et al., 2020; Grozier et al., 2022), Reishi mushroom (Tsuk et al., 2017; Wang et al., 2018) or vitamin D enriched mushroom (Zajak et al., 2020) on global cognitive performance.

To allow for a 10% attrition rate, 80 healthy older adults aged 60-80 years old will be recruited primarily from the University of Reading Ageing Research Panel and the local community. Given the parallel design of the RCT, the cohort will be half split to receive either the control intervention ($N=40$) or the oyster mushroom intervention ($N=40$).

2. Recruitment and Screening

Participants will be initially recruited using opportunity sampling. The study will be advertised via email and posters will be placed around public areas (eg university area, sports hall, library, churches, parkruns, GP practices). Furthermore, participants will be recruited from the Age UK Berkshire and the local community.

Before interested participants are enrolled in our study, they will be invited to attend a familiarisation session to our unit, to determine if they meet the eligibility criteria and they will be given an opportunity to become familiar with the cognitive task battery to reduce the influence of practice effects. Participants will be compensated with £100 for completing all study visits.

3. Inclusion/Exclusion criteria

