In the pre-screening phase, the participants interested in our study will be sent a link to REDCap containing online versions of a Health and Lifestyle Questionnaire and the Epic Norfolk Food Frequency Questionnaire (FFQ). Then, participants, will be contacted to attend a 3-hour familiarisation session at our department, during which the participant's weight, height and blood pressure will be checked, along with a finger-prick, to ensure that the participants are not anaemic. Furthermore, participants will complete the Raven's Progressive Matrices (RPM) measure of fluid intelligence and will perform the cognitive battery tasks twice to control for practice effects in the run up to the test session days. Also, the head and cap size measurements will be taken in a subset of participants (N=20 from each experimental group) that agreed to undertake the EEG at the testing visits.

At the end of the familiarisation visit, participants will be allocated to one of the treatment groups and they will receive a 12-week supply of the intervention powder in sachets. After the familiarisation visit, participants will be asked to follow a low flavonoid diet for 24-hours in advance of the two testing days. In both the baseline and post-visit testing sessions, participants will be instructed to perform several cognitive and mood related tasks. In addition to the behavioural tests, blood pressure, heart rate and body weight will be measured, and electroencephalogram (EEG) measurements will be recorded in a subset of participants using electrodes placed on the scalp for detecting electrical brain activity. Finally at the end of each testing visit, a blood sample will be taken. Each test visit will last approximately 2 hours. **Figure 1** summarises the OYSCOG testing protocol.

[figure not shown]

Figure 1: Study design of the parallel 2-arm OYSCOG RCT, investigating the chronic effects of ergothioneine-rich Pleurotus mushrooms on cognition, cognition, inflammation, and metabolism.

The cognitive-mood battery used will contain the following tasks:

- Positive and Negative Affect Schedule (PANAS-X)- In this mood task, participants are asked to rate their emotion on a 5-point Likert scale, in response to negative emotions (e.g., guilt, fear), positive emotions (e.g., attentiveness, joy) and other affect states (e.g., surprise, shyness).

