All statistical analyses will be performed by using SPSS software. Initially, extreme outliers will be identified and excluded using boxplots (using 3*IQR rule), and subjects with missing data will be excluded from analysis. The main analysis will use a mixed ANOVA to investigate a) the main effect of time (within subject factor, baseline vs 12-weeks), b) the main effect of intervention (between subject factor, placebo vs oyster mushroom group) and c) the intervention*time interaction. For the outcome measures that show significant changes at baseline, a 1-way ANOVA will be applied by treating the baseline scores as a covariate to examine the main effect of intervention. In all analyses, a Bonferroni correction will be examined for post-hoc pairwise comparisons regardless of the significance of the overall F test statistic. Significant comparisons will be reported (*p<0.05, **p<0.01, ***p<0.001).

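### The plan's only reporting rule is tied to significance; nothing commits it to report non-significant comparisons, between-arm differences, confidence intervals or exact p-values

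*Combined protocol and SAP*

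**What the plan says.** Section 6 (Statistical Plan) sets out the analysis in one paragraph. "The main analysis will use a mixed ANOVA" with terms for time, intervention and their interaction. Where an outcome differs significantly at baseline, a one-way ANOVA with the baseline score as covariate is used. The paragraph then says that, in all analyses, "a Bonferroni correction will be examined for post-hoc pairwise comparisons regardless of the significance of the overall F test statistic". It closes with "Significant comparisons will be reported" and a star key with cut-offs at 0.05, 0.01 and 0.001.

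That closing sentence is the only statement in the document about what will be reported. Cohen's d appears in section 1 (Sample Size Calculation) as a planning value and is not mentioned as a quantity to be estimated. Section 6 names no primary outcome, and section 5 (OYSCOG study Protocol) lists nine task entries in the cognitive and mood battery.

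**The concern.** Pairwise comparisons are to be run whatever the overall F test shows, and significance is then the only stated criterion for reporting them. A results section that lists starred comparisons and nothing else would follow this plan to the letter.

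Three things would then be lost. Estimates that pass a significance threshold in a trial of this size are on average too large. A comparison that is not shown cannot be judged as an informative null or merely an imprecise one. And with nine tasks and no named primary outcome, the reader could not tell how many comparisons stood behind the few displayed.

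**Working it through.** **Setting the text side by side.** The sentence on pairwise comparisons applies to all analyses and does not depend on the F test. The next sentence gives significance as the condition for reporting. No other sentence requires an estimate, an interval, an exact p-value or a null result. Section 6 is a continuous paragraph with no gap or redaction, so the silence belongs to the plan. Omitting null comparisons is therefore permitted, though not prescribed.

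**Inputs.**
- From section 1: alpha 0.05 (sidedness not stated); d = 0.60; a value of 0.80 printed as beta and read here as power; "72 participants should give sufficient statistical power"; "To allow for a 10% attrition rate, 80 healthy older adults aged 60-80 years old will be recruited"; and equal allocation ("the cohort will be half split to receive either the control intervention").
- From section 5: the EEG subset, "N=20 from each experimental group".
- Assumed, not in the documents: true effects of d = 0.2, 0.3 and 0.4; two-sided testing at 0.05; a simple two-arm t test standing in for the planned ANOVA.

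**The plan's own figure first.** Per arm, n = 2(z_alpha + z_power)²/d².
- One-sided: 2(1.645 + 0.842)²/0.36 = 34.3, so 35 per arm and 70 in total. The exact t-test calculation gives 36 per arm, which is the plan's 72.
- Two-sided: 2(1.960 + 0.842)²/0.36 = 43.6, so 44 per arm and 88 in total; 90 with the t test.
- Attrition: 72/0.90 = 80, as stated.

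So 72 reproduces with a one-sided test. Two-sided, 72 evaluable participants give 71% power at d = 0.60.

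**Smallest result that can earn a star.** With n per arm, the standard error of the difference in SD units is √(2/n). For n = 36 it is √(2/36) = 0.236. The critical t on 70 degrees of freedom is 1.994, so the observed |d| must reach 1.994 × 0.236 = 0.47. For n = 20 the threshold is 2.024 × 0.316 = 0.64.

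**Average size of results that pass.** Simulation of the two-arm t test, 2 million draws per setting, 36 per arm, mean absolute difference among significant results in true-SD units:

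| True d | Power | Mean if significant | Ratio to truth |
|---|---|---|---|
| 0.60 (planned) | 71% | 0.71 | 1.19 |
| 0.40 (assumed) | 39% | 0.63 | 1.57 |
| 0.30 (assumed) | 24% | 0.60 | 2.00 |
| 0.20 (assumed) | 13% | 0.58 | 2.88 |

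If the difference is divided by the sample SD instead, the mean significant d is 0.72 at a true 0.60 and 0.62 at a true 0.30, so the ratios barely change.

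**Hand check.** For a normal estimate kept only when it exceeds c, the mean is d + se × φ(a)/(1 − Φ(a)), with a = (c − d)/se.
- d = 0.60: a = (0.470 − 0.60)/0.2357 = −0.551; 0.60 + 0.2357 × 0.3427/0.7092 = 0.714; ratio 1.19.
- d = 0.30: a = 0.722; 0.30 + 0.2357 × 0.3075/0.2353 = 0.608; ratio 2.03.

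Both agree closely with the simulation.

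**Sensitivity to sample size.** With all 80 retained (40 per arm), the ratios at d = 0.60, 0.40, 0.30 and 0.20 are 1.15, 1.51, 1.91 and 2.75. In the EEG subset (20 per arm) they are 1.45, 2.01, 2.59 and 3.76.

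**The case against.** The strongest reply is that the sentence excludes nothing. The word *only* is absent, and with its three star levels the sentence can be read as a key to table notation. It also comes straight after the post-hoc comparisons, and the plan does not say that the mixed ANOVA terms will be withheld when they are not significant. All of this stands. A reader might infer that the plan announces the suppression of null results and that the trial's reported effects are therefore exaggerated. The text does not support that: both consequences depend on how the sentence is applied.

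What the reply does not do is supply the missing commitment. Even read as a notation key, the sentence leaves the plan with no statement that estimates, intervals or null comparisons will be given. Nor do the ANOVA terms fill the gap, because an F test by itself gives neither the direction nor the size of an effect, and no reporting commitment is made for those terms either.

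A second reply concerns size. At the only effect in the documents, d = 0.60, the inflation is about 1.2 times, which is modest; the larger ratios rest on assumed smaller effects. This also stands. The t test is a simplification as well: Bonferroni correction would raise the threshold and the inflation, while adjustment for baseline would raise power and reduce it.

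A reader might also want to add the familywise error rate. If the battery is counted as 13 independent scores, the chance of at least one false positive at 5% is 1 − 0.95^13 = 0.487. That figure does not belong to this point. The documents list tasks, not analysed scores, so 13 is a reviewer's count; correlation lowers the result (about 42% or 33% under assumed common correlations of 0.3 or 0.5); and it measures multiplicity, which a reporting rule leaves unchanged. Full reporting would only let the reader see the number of comparisons.

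**Conclusion.** The point holds as a gap in commitment. Significance is the sole stated reporting criterion, and the plan permits a report made up only of starred comparisons. It does not require one, so omitted nulls and inflated effects are risks and not stated outcomes.

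If non-significant comparisons were omitted, the surviving effects would be overstated by about 1.2 times at the planned d = 0.60 and by about 2 to 3 times at a true d of 0.3 to 0.2, and by more in the EEG subset. These figures assume 36 evaluable per arm, a two-sided 5% level and a simple two-arm t test. The plan should be changed because the correction is nearly free and removes the ambiguity, but the point does not call the design or the main analysis into question.

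**What to change.** Replace the closing sentence of section 6 with:

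> For every outcome and every pairwise comparison run, the estimated difference, its 95% confidence interval and the exact p-value will be reported, whether or not significant.

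Stars may stay as a display aid.

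As a separate change, to be labelled as a change to the analysis, give the between-arm difference at 12 weeks adjusted for baseline for every outcome with a baseline measure. At present that adjustment is planned only for outcomes with significant baseline differences. The reporting fix does not depend on it.

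The cost is longer results tables and, for the second change, a little more analysis work. No new data are needed.
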